- HOLD pazopanib AND CONTINUE BP monitoring at least once a day until BP returns to grade 0-1,
- Then resume pazopanib at same dose.

THIS ELEVATED BP WILL NOT BE CONSIDERED AN AE UNLESS THERE IS A SECOND OCCURRENCE WHILE TAKING BP MEDICATIONS REGULARLY.

3.3.6.3 Management of QT Prolongation and Torsade de Pointes:

In clinical studies with pazopanib, events of QT prolongation or Torsade de Pointes have occurred. Pazopanib should be used with caution in patients with a history of QT interval prolongation, patients taking antiarrythmics or other medications that may potentially prolong QT interval, or those with relevant pre-existing cardiac disease. When using pazopanib, baseline and periodic monitoring of electrocardiograms and maintenance of electrolytes (calcium, magnesium, potassium) within normal range is recommended.

3.3.6.4 Management of Arterial Thrombotic Events:

In clinical studies with pazopanib, myocardial infarctions, angina, ischemic stroke and transient ischemic attack were observed. Fatal events have been observed. Pazopanib should be used with caution in patients who are at increased risk of thrombotic events or who have had a history of thrombotic events. Pazopanib has not been studied in patients who have had an event within the previous 6 months. A treatment decision should be made based upon the assessment of individual patient's benefit/risk.

3.3.6.5 Management of Hemorrhagic Events:

In clinical studies with pazopanib hemorrhagic events have been reported. Fatal hemorrhagic events have occurred. Pazopanib has not been studied in patients who had a history of hemoptysis, cerebral, or clinically significant gastrointestinal hemorrhage in the past 6 months. Pazopanib should be used with caution in patients with significant risk of hemorrhage.

Version Date: 07/17/2025 Page 25 of 96

3.3.6.6 Management of Gastrointestinal Perforations and Fistula:

In clinical studies with pazopanib, events of gastrointestinal (GI) perforation or fistula have occurred. Fatal perforation events have occurred. Pazopanib should be used with caution in patients at risk for GI perforation or fistula.

3.3.6.7 Wound Healing issues:

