- 6.4.1.4.5 Progression: 25% increase in the sum of products of all measurable lesions over smallest sum observed (over baseline if no decrease) using the same techniques as baseline, OR clear worsening of any evaluable disease, OR appearance of any new lesion/site, OR clear clinical worsening or failure to return for evaluation due to death or deteriorating condition (unless clearly unrelated to this cancer). Patients will also be considered to have progressive disease if there is significant increase in T2/FLAIR non-enhancing lesions AND clinical progression. (See section 6.4.1 and 6.3.7 for definitions). To be considered progressive disease, increase in T2/FLAIR should occur on stable or increasing doses of corticosteroids compared to baseline scan or best response following initiation of therapy, and should not be due to co-morbid events (e.g. radiation therapy, demyelination, ischemic injury, infection, seizures, post-operative changes, or other treatment effects).
- 6.4.1.4.6 Unknown: Progression has not been documented and one or more measurable or evaluable sites have not been assessed.
- 6.4.2 Best Response: This will be calculated from the sequence of objective statuses.

For patients with all disease sites assessed every evaluation period, the best response will be defined as the best objective status as measured according to Section 6.4.1. If the response does not persist at the next regular scheduled MRI, the response will still be recorded based on the prior scan, but will be designated as a non-sustained response. If the response is sustained, e. g. still present on the subsequent MRI, it will be recorded as a sustained response, lasting until the time of tumor progression. Best response is unknown if the patient does not qualify for a best response or increasing disease and if all objective status determinations before progression are unknown.

- 6.4.3 Neurological Exam: Although not used for determining response, it is useful to evaluate improvement in the neurologic exam, (as compared to the baseline assessment), that should coincide with objective measurement of tumor size.
 - +1 Better
 - 0 Unchanged
 - -1 Worse
 - B Baseline

Version Date: 07/17/2025 Page 37 of 96

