6.5 TOXICITY CRITERIA

The following adverse event management guidelines are intended to ensure the safety of each patient while on the study. The descriptions and grading scales found in the revised NCI Common Terminology Criteria for Adverse Events (CTCAE) version 4.0 will be utilized for AE reporting. All appropriate treatment areas should have access to a copy of the CTCAE version 4.0. A copy of the CTCAE version 4.0 can be downloaded from the CTEP web site (http://ctep.cancer.gov/protocolDevelopment/electronic_applications/ctc.htm#ctc_40).

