8.6 GUIDELINES FOR REPORTING SERIOUS ADVERSE EVENTS TO BTTC

What to Report?	When to Report?
All Deaths, except that due to progressive disease, occurring from the time the consent is signed through 30 days after the last day of active treatment	Within 1 working day (24 hours) from the time the research team becomes aware of event

Version Date: 07/17/2025 Page 42 of 96

What to Report?		When to Report?		
A de	ther Serious Unexpected Suspected dverse Reactions (that did not result in eath) occurring from the time the onsent is signed through 30 days after the last day of active treatment	Within 5 working days from the time the research team becomes aware of event		
	Il protocol deviations, non-compliance nd unanticipated problems	Within 5 working days from the time the research team becomes aware of event		
ad or fo in ter pr	regnancy, although not itself a serious diverse event, should also be reported in a serious adverse event form and be followed up to determine outcome, acluding spontaneous or voluntary ermination, details of birth, and the resence or absence of any birth defects it congenital abnormalities.	Within 5 working days from the time the research team becomes aware of event		

The CCR problem report form will be used to submit adverse events to BTTC. See Appendix 15.9. Participating centers must also submit the report to their IRB in accordance with their institutional policies.

The BTTC Coordinating Center will maintain documentation of all Serious Adverse Events from each institution. The BTTC Coordinating Center will notify all investigators of any serious and unexpected adverse experiences that are possibly related to the study agent/s. The investigators are to file a copy with their protocol file and send a copy to their IRB according to their local IRB's policies and procedures.

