We will monitor the toxicity based on the combined data from the above two cohorts with a total sample size of 66. All grade 3 or greater toxicities attributable to the study treatment will be counted. Accrual will be temporarily suspended for analysis after each of the following interim accrual goals. We will monitor the toxicity when the accrual is 5, 10, 20, 35, and 50 based on using the following stopping rule: if the posterior probability of toxicity greater than 0.3 is greater than 0.95 (i.e., Pr (toxicity>0.3|data) >0.95), we terminate the study for toxicity. Assuming the beta prior Beta (0.6, 1.4) for the toxicity, we have the following operating characteristics.

Operating characteristics of the proposed stopping rule

True toxicity probability	0.2	0.3	0.4	0.5
Stopping Probability	1.3%	12.4%	55.0%	92.7%
Average number of patients	65.3	60.3	43.9	24.2
treated				

We obtain the following stopping boundary: the study will be terminated if we observe $\geq 4/5$, 6/10, 10/20, 16/35, 21/50 (# of patients experienced DLTs/# of patients treated). Note that our safety monitoring starts with a small cohort size of 5, and then gradually increases to 15. Therefore, if the treatment agents are overly toxic, the trial will stop before exposing many patients to toxicities.

Patient-reported outcomes: The sample size for this trial was based on the primary endpoint of the study.

Received MDASI-BT forms will be checked versus the timing schedule and considered as valid if they fall within ten days of the scheduled assessment. Compliance rates will be calculated as the number of received valid forms over the number of expected forms. Differences between groups in compliance will be tested by use of Fisher's exact test at every time point.

We will use descriptive statistics to describe how patients rate symptom severity and interference with function at each time point. Error bar graphs for each of the symptoms will be constructed at each time point. The proportion of patients rating their symptoms to be 7 or greater (on a 0-10 scale) will also be reported. We will construct individual patient profiles for each of the selected symptoms to describe the individual patients' patterns of change over time. We will calculate the

Version Date: 07/17/2025 Page 44 of 96

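### The Section 9 toxicity rule gives a treatment-related death the same weight as any grade 3 event, and no death triggers an accrual pause between the scheduled looks or after patient 50.

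*Combined protocol and SAP*

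**What the plan says.** Section 9 pools Groups A and B (66 patients) for safety. The event is defined in one sentence: "All grade 3 or greater toxicities attributable to the study treatment will be counted". Section 6.5 sets the grading scale: "Common Terminology Criteria for Adverse Events (CTCAE) version 4.0 will be utilized for AE reporting". The study terminates "if the posterior probability of toxicity greater than 0.3 is greater than 0.95", and the prior is given as "Assuming the beta prior Beta (0.6, 1.4) for the toxicity". The boundary is introduced with "We obtain the following stopping boundary: the study will be terminated if we observe" and is then listed as 4/5, 6/10, 10/20, 16/35 and 21/50. Accrual is paused for an analysis at each of these five accrual counts, whatever has happened. No look is planned after patient 50.

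Other provisions that bear on deaths:

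- **Section 9** states that a formal DSMB review is not needed and assigns monitoring to the Academic PI and the study statistician.
- **Section 7.3.1** provides a team teleconference every other week, PI review of each patient's adverse events, and immediate reporting of safety concerns to the IRB.
- **Section 7.3.3** provides SMC review about once a year, or more often if the SMC requires it.
- **Section 8.6** requires a report within one working day for "All Deaths, except that due to progressive disease, occurring from the time the consent is signed"; the window closes 30 days after treatment ends.
- **Section 3.3.6.14** removes the individual patient from study after a life-threatening toxicity.

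None of these attaches a consequence for accrual to a death.

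**The concern.** A 30% tolerance can be reasonable for reversible grade 3 events. It is hard to defend as the only prespecified limit on fatal ones, and the protocol treats fatal toxicity as foreseeable. Of hemorrhage on pazopanib, Section 3.3.6.5 says: "Fatal hemorrhagic events have occurred". Sections 3.3.6.1 to 3.3.6.12 also mention fatal hepatic failure, arterial thrombotic events, gastrointestinal perforation, neutropenic colitis and interstitial lung disease.

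Because the count is pooled, a death moves the study no closer to termination than a grade 3 laboratory abnormality would. Deaths between looks (for example among patients 21 to 34 or 36 to 49), or after patient 50, prompt no pause. At stake is whether patients continue to be enrolled before an independent group has considered a treatment-related death.

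**Working it through.** **Inputs (all Section 9).** Limit 0.3, posterior cut-off 0.95, prior Beta(0.6, 1.4), looks at n = 5, 10, 20, 35 and 50, maximum N = 66.

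**Step 1: reproduce the boundary.** With x affected patients among n, the posterior is Beta(0.6 + x, 1.4 + n − x). The boundary is the smallest x with Pr(p > 0.3 | data) > 0.95.

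| n | Largest x that does not stop | Posterior | Smallest x that stops | Posterior |
|---|---|---|---|---|
| 5 | 3 | 0.875 | 4 | 0.975 |
| 10 | 5 | 0.880 | 6 | 0.962 |
| 20 | 9 | 0.906 | 10 | 0.961 |
| 35 | 15 | 0.938 | 16 | 0.970 |
| 50 | 20 | 0.926 | 21 | 0.959 |

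The fourth column is the protocol's boundary exactly.

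**Step 2: reproduce the operating characteristics.** Exact binomial recursion over the five looks:

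| True toxicity | P(stop), stated | P(stop), recomputed | Average N, stated | Average N, recomputed |
|---|---|---|---|---|
| 0.2 | 1.3% | 1.3% | 65.3 | 65.3 |
| 0.3 | 12.4% | 12.3% | 60.3 | 60.4 |
| 0.4 | 55.0% | 54.1% | 43.9 | 44.1 |
| 0.5 | 92.7% | 92.4% | 24.2 | 24.4 |

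Agreement is close. Adding a look at 66 fits worse (61.7% at 0.4), which confirms that the stated figures assume no look after 50.

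**Step 3: apply the rule to deaths.** The second column of Step 1 is also the largest number of treatment-related deaths with which the rule lets accrual resume: 3/5, 5/10, 9/20, 15/35 and 20/50. This assumes that a fatal event is graded above 3 and so falls within the count. Section 9 refers to toxicities in one sentence and to patients with DLTs at the boundary; neither reading gives a death extra weight.

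**Step 4: size under assumed death rates d.** The documents give no treatment-related death rate for this combination in glioblastoma, so a range is shown. Expected deaths are 66 × d. The chance of at least three is the binomial upper tail with n = 66, ignoring early stopping. The chance of at least one in the first 20 patients is 1 − (1 − d)^20.

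| d (assumed) | Expected deaths in 66 | P(at least 3 in 66) | P(at least 1 in first 20) |
|---|---|---|---|
| 1% | 0.7 | 3% | 18% |
| 2% | 1.3 | 15% | 33% |
| 5% | 3.3 | 65% | 64% |
| 10% | 6.6 | 97% | 88% |

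**Step 5: what the existing rule does.** Its stopping probability depends only on total attributable grade 3 or greater toxicity. At 15% (for example 5% fatal plus 10% other) the Step 2 recursion gives 0.3%. At 20% (for example 10% fatal plus 10% other) it gives 1.3%. These splits are illustrations.

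**The case against.** The case on the other side has real substance.

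- **Accrual does pause.** A reader might infer that the trial could enrol through a run of deaths with no required pause. Section 9 does not support that: it suspends accrual at all five looks, three of them by patient 20. What remains is that the pauses follow the accrual count and not events, none comes after patient 50, and the only stated criterion at each is the pooled 30% limit.
- **Deaths need not go unseen.** Sections 7.3.1 and 8.6 provide frequent team review, immediate IRB reporting of safety concerns and rapid reporting of non-progression deaths. Section 8.5 sends serious adverse events to the manufacturer within 24 hours. Section 11.3 speaks of checking for severe toxicity that would preclude further enrolment, although it is worded for dose levels and has no criterion. Sections 7.1 and 7.2 also rely on NIH policies that are not reproduced, so what those require after a related death is unknown. This stands as evidence that a hold is possible, not that the protocol requires one.
- **There is no demonstrated reporting loophole.** A reader might combine the Section 8.6 exemption for deaths from progressive disease with the progression definition in Section 6.4.1.4.5, and conclude that an unexplained death escapes reporting. The documents do not support this. Section 6.4.1.4.5 defines response status, Section 8.6 does not cite it, and Section 8.2 governs causality.
- **The higher death rates are unsupported.** A death rate from sepsis of 1% is reported for oral topotecan alone in lung cancer (Section 13.1.10.2.1.1). That is one cause in another population and not an upper bound, but it is why the range starts at 1%. There, three or more deaths are unlikely.
- **Pooling grades is a legitimate choice,** and its operating characteristics are disclosed. This stands, and it is why no numeric death limit is proposed here.

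**Conclusion.** The point holds in this form: Section 9 has no death-specific criterion, no death triggers a pause between looks or after patient 50, and at the looks the rule lets accrual resume with up to 3/5, 5/10, 9/20, 15/35 or 20/50 treatment-related deaths. Oversight elsewhere leaves a hold to discretion. The protocol's calculations are sound; the limitation is in what they count.

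The practical size depends on an unknown death rate. At 1% to 2% the gap would seldom involve several deaths; at 5% to 10% three or more become likely, while the pooled rule would almost never stop if total toxicity is 15% to 20%. The figures treat patients as independent with a constant risk. They illustrate the rule's behaviour and do not predict deaths in this trial. The case for change does not depend on the higher rates: the safeguard is cheap, and even one treatment-related death warrants a required review.

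**What to change.** Add one sentence to Section 9: any death judged at least possibly related to study treatment under the Section 8.2 causality assessment suspends accrual in both cohorts, at any time including after patient 50, until the existing SMC has reviewed it. Section 7.3.3 already permits reviews more often than annually, so no new committee is needed. The pooled boundary, its operating characteristics and the sample size stay as they are.

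The cost is an occasional accrual pause and an ad hoc SMC review. The chance of at least one such pause within the first 20 patients is 18%, 33%, 64% and 88% at assumed death rates of 1%, 2%, 5% and 10%, in addition to the scheduled looks. Whether to add a numeric limit on deaths, and at what level, is for the sponsor to decide.

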2.3.4 Initiation of Therapy

Treatment may not be initiated until the participating institution receives a faxed or emailed copy of the patient's Registration Verification Letter from the Central Registration Office.

All Patients that are eligible to receive therapy must initiate treatment within 96 hours after the registration.

The BTTC Coordinating Center must be notified in writing of any exceptions to this policy.

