3.4 ON STUDY EVALUATION

3.4.1 General Requirements

- 3.4.1.1 CBC with differential and platelets and serum chemistries and LFTs (ALT, AST and bilirubin) will be performed every two weeks X 2, (+/- 3 days) then every 4 weeks (+/- 3 days) prior to each cycle during treatment. UPC (+/- 3 days) will be done monthly prior to each cycle.
- 3.4.1.2 A brain MRI/CT for group B will be done monthly until 3 months then every other month thereafter, for group A scan will be obtained every other month prior to initiation of odd numbered 28 days treatment cycles (+/- 3 days).
- 3.4.1.3 All relevant information regarding drug doses, concomitant medications, and doses, measurable lesions with measurements, tumor response, laboratory examinations, and treatment-related toxicities shall be documented in the patient's medical record and flow sheets.
- 3.4.2 A complete Neurologic exam (to include documentation of the patients Karnofsky Performance Status) will be performed prior to every evaluation where an MRI is scheduled. The MDASI-BT (Appendix 15.5) will be completed at baseline and at the time of each evaluation that includes an imaging study.
- 3.4.3 The patient will complete the MDASI-BT (see Appendix 15.5) at the time of clinical evaluation with MRI as long as the clinical therapy is being administered, unless clinical deterioration makes self-report not possible before that time. The time when patients are unable to complete the self-report questionnaires will be used as part of the study analysis. The MDASI-BT will be completed only by the patient, unless changes in vision

Version Date: 07/17/2025 Page 27 of 96

or weakness make this difficult. If this occurs, then the caregiver or research assistant may read the questions to the patient or assist with marking the severity number or score as described by the patient. A patient caregiver may complete the questionnaires as a patient-preference proxy if the patient's deficits preclude self-report.

- 3.4.3.1 A measurement of BP should be taken twice weekly for the first 2 months of therapy, then weekly for 2 months, and then once per month thereafter as detailed in 3.3.5.2. BP can be assessed by any method (i.e., at home or by another physician) as long as the treating physician is informed of the measurement, verifies any measurement that is not normal and takes appropriate action.
- 3.4.3.2 Thyroid function test (T4 and TSH) (+/- 3 days) are to be monitored every 8 weeks (+/- 3 days)

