3.4.4 Follow-up

Patients will be evaluated for adverse events at the end of each cycle. In addition, all serious adverse events will be reported to the NCI BTTC as in section 8.6.

All patients will be followed for overall survival, when possible.

Patients who discontinue treatment due to progression will be followed for survival every 3 months.

Patients who come off therapy for reasons other than progression should be followed until progression or institution of new anti-tumor therapy. They should then be followed for survival.

3.5 **QUESTIONNAIRES**

The MDASI-BT will be utilized for this portion of the study. Full instruments are provided in the Appendix 15.5 In addition, information regarding demographics and treatment history will be collected as part of the larger study and used in this analysis.

The MDASI-BT consists of 23 symptoms rated on an 11-point scale (0 to 10) to indicate the presence and severity of the symptom, with 0 being "not present" and 10 being "as bad as you can imagine." Each symptom is rated at its worst in the last 24 hours. Symptoms included on the instrument include those commonly associated with cancer therapies, those associated with increased intracranial pressure, and those related to focal deficits. The questionnaire also includes ratings of how much symptoms interfered with different aspects of a patient's life in the last 24 hours. These interference items include: general activity, mood, work (includes both work outside the home and housework), relations with other people, walking, and enjoyment of life. The interference items are also measured on 0 - 10 scales. The average time to complete these instruments is 5 minutes. The MDASI-BT has been translated into 18 languages [17, 20]

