9 STATISTICAL CONSIDERATIONS

For this study, since there is experience with the drug combination a formal DSMB review will not be necessary.

Time to progression and overall survival will be evaluated using the Kaplan-Meier product-limit survival curve methodology. Six-month Progression Free Survival (PFS) will be estimated using Kaplan-Meier estimates and associated two-sided 95% confidence intervals.

Recurrent glioblastoma with no prior exposure to bevacizumab cohort (Group A): A maximum of 34 patients will be observed in a two-stage Simon optimum design. In the first stage, 9 patients will be accrued. If two or more patients are progression-free at 6 months (PFS6), an additional 25 patients will be accrued. We halt registering patients after 9 patients until we have at least 2 patients are progression free at six months. If 9 or more out of 34 have PFS6, then the study will be declared promising. This study has a 5% chance of declaring promise if the PFS6 rate is at most 15%. It has an 80% chance of declaring promise if the PFS rate is at least 35%.

Recurrent glioblastoma with prior exposure to bevacizumab cohort (Group B): In the group that failed bevacizumab, a maximum of 32 patients will be observed in a two-stage Simon

Version Date: 07/17/2025 Page 43 of 96

optimum design. In the first stage, 14 patients will be accrued. If one or more patients is progression-free at 3 months (PFS3), an additional 18 patients will be accrued. We will halt registration after 14 patients until at least 1 patient is progression free at 3-months. If 2 or more out of 32 have PFS3, then the study will be declared promising. This study has a 5% chance of declaring promise if the PFS3 rate is at most 1%. It has an 80% chance of declaring promise if the PFS rate is at least 12%.

In both patient cohorts, for patients who drop out for reasons other than PD or toxicity, we will replace them. We expect the dropout rate to be not more than 10%, therefore in general it is not an issue to implement the design. The patients who drop out due to toxicity will be counted as treatment failure when implementing the Simon's two stage design and assessing the 6-month PFS rate in either cohort.

The trial will be monitored by the Academic PI, [name], and the study statistician, [name].

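### Section 9 times toxicity looks by accrual and does not require completed follow-up, so the tabulated stopping probabilities are not secured

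*Combined protocol and SAP*

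**What the plan says.** Section 9 monitors toxicity on both cohorts pooled, with a total of 66 patients. The looks are set by accrual: "We will monitor the toxicity when the accrual is 5, 10, 20, 35, and 50". On the pause it says: "Accrual will be temporarily suspended for analysis after each of the following interim accrual goals". It gives no pause length and no follow-up condition.

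The counted event is described as: "All grade 3 or greater toxicities attributable to the study treatment will be counted". No period is attached. The trial stops if the posterior probability that the toxicity rate exceeds 0.3 is above 0.95, under a Beta(0.6, 1.4) prior. The resulting boundary is 4/5, 6/10, 10/20, 16/35 and 21/50, expressed as "of patients experienced DLTs/# of patients treated". The table gives stopping probabilities of 1.3%, 12.4%, 55.0% and 92.7% at true rates of 0.2, 0.3, 0.4 and 0.5.

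Other sections bear on when a patient's outcome becomes known:

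- Section 2.3.4: patients "must initiate treatment within 96 hours after the registration".
- Section 3.4.1: blood counts, chemistries and liver tests "will be performed every two weeks X 2, (+/- 3 days) then every 4 weeks".
- Section 3.4.4: "Patients will be evaluated for adverse events at the end of each cycle".
- Section 6.1.2: cycle data may be entered up to 40 days after day 1 of the cycle.
- Section 3.3: treatment may continue for up to one year.

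The term DLT is not defined for this trial. The only definition, in Section 1.2.4, describes the earlier phase I study.

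Section 9 also says that "for patients who drop out for reasons other than PD or toxicity, we will replace them". It does not say whether a replaced patient stays in the toxicity count.

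**The concern.** The boundary compares events seen with patients treated. A patient registered just before a look is in the denominator at once but may not yet have had time to have an event, or to have it recorded. Treating that patient as event-free pulls the observed rate down, so the boundary is harder to reach than the table assumes.

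This is the only toxicity rule in the plan with a numeric threshold. Section 9 dispenses with formal DSMB review. The every-other-week teleconference (Section 7.3.1) and the Safety Monitoring Committee (Section 7.3.3) have no stated limit. The accrual halts in the Simon designs depend on efficacy within each cohort and are not tied to the toxicity looks. A reader of the table would expect a 55% chance of stopping at a true rate of 40%. The written rule could deliver less, with more patients treated before the trial stops.

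**Working it through.** **Inputs (Section 9).** Looks at n = 5, 10, 20, 35, 50; maximum 66; prior Beta(0.6, 1.4); stop if Pr(rate > 0.3 | data) > 0.95.

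**Step 1: the boundary.** After x events in n patients the posterior is Beta(0.6 + x, 1.4 + n − x). The boundary is the smallest x whose upper tail above 0.3 exceeds 0.95.

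| n | x | Tail at x | Tail at x − 1 |
|---|---|---|---|
| 5 | 4 | 0.975 | 0.875 |
| 10 | 6 | 0.962 | 0.880 |
| 20 | 10 | 0.961 | 0.906 |
| 35 | 16 | 0.970 | 0.938 |
| 50 | 21 | 0.959 | 0.926 |

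The printed boundary is reproduced exactly.

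**Step 2: the table, with every outcome known at each look.** An exact binomial recursion carries the event count from look to look and removes the probability at or above the boundary. At a true rate of 0.4 the five looks stop 8.70%, 10.59%, 12.01%, 10.19% and 12.56% of trials, 54.05% in all. Mean patients treated = 5(0.0870) + 10(0.1059) + 20(0.1201) + 35(0.1019) + 50(0.1256) + 66(0.4595) = 44.1.

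| True rate | Stop, computed | Stop, stated | Mean N, computed | Mean N, stated |
|---|---|---|---|---|
| 0.2 | 1.3% | 1.3% | 65.3 | 65.3 |
| 0.3 | 12.3% | 12.4% | 60.4 | 60.3 |
| 0.4 | 54.0% | 55.0% | 44.1 | 43.9 |
| 0.5 | 92.4% | 92.7% | 24.4 | 24.2 |

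Agreement is within one percentage point and 0.3 patients, but only with complete outcomes.

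**Step 3: last patient still pending.** Assume that the pause adds no follow-up, the last patient at each look shows no event yet, all earlier patients are complete, and the pending outcome is used at the next look. At the first look, with a true rate of 0.4:

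- Complete data: Pr(at least 4 of 5) = 5(0.4⁴)(0.6) + 0.4⁵ = 0.0768 + 0.0102 = 0.0870.
- One pending: all four others must have events, 0.4⁴ = 0.0256.

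Over all five looks:

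| Pending patients | Stop at 0.4 | Stop at 0.5 | Mean N at 0.4 | Mean N at 0.5 |
|---|---|---|---|---|
| None | 54.0% | 92.4% | 44.1 | 24.4 |
| 1, half of eventual events visible | 50.8% | 91.2% | 46.4 | 26.8 |
| 1, none visible | 46.9% | 89.7% | 49.0 | 29.4 |
| 2, none visible | 40.3% | 86.5% | 52.9 | 34.1 |
| 3, none visible | 34.4% | 82.8% | 55.8 | 38.2 |

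**Step 4: effect of the pause.** Simulation with Poisson accrual at 2 to 4 patients a month and event onset uniform over 28 days. Both are assumptions, since the documents give neither. Stopping at a true rate of 0.4:

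- no pause: about 36 to 42%;
- 14-day pause: about 48 to 50%;
- 28-day pause, equal to the assumed onset period: about 54%, which restores the complete-data result.

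**The case against.** The strongest reply is that accrual is suspended at every look, so outcomes mature while nobody enrols. That is right as far as it goes: a pause as long as the onset period restores the table. But the suspension is for analysis, with no stated length and no follow-up condition, so the text does not secure such a pause.

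The pending-patient figures are also open to challenge. They assume a pause that adds nothing and a last patient with nothing visible. Early surveillance is better than that picture suggests: blood pressure is checked twice weekly from the start (Section 3.3.6.2.1) and each patient is discussed every other week. If half of the last patient's eventual events are visible, the shortfall at 40% is about 3 points rather than 7. And if a boundary crossed during the pause is acted on at once, the stop is delayed rather than lost. All this stands, so the figures are illustrations and not estimates for this trial.

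A reader might infer that the table is wrong. It is not; both it and the boundary reproduce.

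A reader might also infer that the missing window makes the rule stop too often, because year-long counting is set against a limit meant for cycle 1. The documents do not support that. Nothing makes 0.3 a cycle-1 limit, and Section 9 counts all attributable grade 3 or greater toxicities. The cycle-1 definition belongs to the phase I study and is not adopted here.

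Nor do the 18-week figures in Sections 3.3.6.1 and 3.3.6.2 show how late qualifying events occur in this trial. They come from pazopanib studies, one covers any grade, and the other uses a blood-pressure threshold different from this trial's grade 3.

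**Conclusion.** The concern holds as a gap in the rule, not an error in its arithmetic. An accrual trigger with patients treated as the denominator does not by itself deliver the tabulated probabilities. They require known outcomes for all counted patients, and no section secures that. The omission is certain; its size is not.

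The likely direction is under-stopping or delayed stopping of a regimen that is too toxic. With one uninformative patient at each look and no useful follow-up during the pause, stopping falls from 54.0% to 46.9% at a true rate of 40% and from 92.4% to 89.7% at 50%, with about five more patients treated on average in each case. A short pause under the assumed accrual and onset gives a loss of similar order. A pause that covers the onset period removes it.

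The undefined term DLTs and the silence on replaced patients are smaller gaps in the same rule. Section 9 should be amended, because this is the plan's only numeric toxicity limit.

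**What to change.** In Section 9:

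1. Define the counted event once: a patient's first attributable CTCAE grade 3 or greater toxicity within a stated window. The sponsor should choose and justify the window, and state that the 0.3 limit and the table refer to the rate within it.
2. Keep accrual suspended at each look until all n patients have completed the window or had the event. The printed boundary and table then stand. Alternatively, use evaluable patients as n, defined by time since enrolment and not by outcome, and recompute the boundary and table. With two patients not yet evaluable the boundary becomes 3/3, 5/8, 9/18, 15/33, 20/48, and stopping at a true rate of 30% becomes 14.65% rather than 12.3%. The first look would also need a minimum evaluable number, since two evaluable patients can never stop the trial.
3. Replace DLTs in the boundary with this event.
4. State that replaced patients who were treated stay in the toxicity denominator, or say otherwise how they are counted.

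The cost is protocol wording, a justification of the window, and longer pauses at up to five looks where accrual is already suspended. For a 28-day window each pause is about 4 to 6 weeks: 28 days of follow-up at least, or up to 40 days if data entry takes the full time allowed. That is 20 to 30 weeks if all five looks occur and none overlaps a Simon halt. A longer window costs proportionately more, which is the main reason to consider the evaluable-patient option.
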